6.3.3.4 Acute Migraine Medication days per Month

Acute migraine medication days per month are assessed analogously to acute migraine-specific medication days per month (see Section 6.3.2.2).

An acute migraine medication day is defined in Section 9.2.3.

The number of acute migraine medication days per month in the DBT and OLE Phases is prorated to 28 days.

Acute Migraine Medication Days per Month in the DBT Phase

Analyses are based on the DBT migraine analysis set with eDiary efficacy dates in the on-DBT efficacy analysis period.

Descriptive Analyses

The table of the number of acute migraine medication days per month in the DBT Phase is provided, and has the same format as the one described in Section 6.3.2.2.

Treatment Group Comparisons

Treatment groups are compared using a linear mixed effects model with repeated measures with the same properties as the model specified in Section 6.3.2.2, except that the number of acute migraine medication days per month is the dependent variable.

Results support exploratory objective #6.

Acute Migraine Medication Days per Month in the OLE Phase

Analyses are based on the OL rimegepant migraine analysis set with eDiary efficacy dates in the on-OL rimegepant efficacy analysis period.

The table of the number of acute migraine medication days per month in the OLE Phase is provided, and has the same format as the one described in Section 6.3.2.2.

Results support exploratory objective #7.

6.3.3.5 Medication Days per Month on Planned OL Rimegepant Dosing Days

This section includes analyses which are not formally prespecified in Section 3.2.3, but are typically included for migraine prevention studies with an OLE Phase.

Planned OL rimegepant dosing days are defined in Section 9.4. Medications are OL rimegepant and acute migraine medication.

For a given medication, the medication days per month on planned scheduled OL rimegepant dosing days through Month 10 is calculated as: $14 \times (\text{total number of medication days on the same days as planned scheduled OL rimegepant dosing days through Month 10 in the on-OL rimegepant efficacy analysis period)/(total number of planned scheduled OL rimegepant dosing days through Month 10 in the on-OL rimegepant efficacy analysis period).$

For a given medication, the medication days per month on planned non-scheduled OL rimegepant dosing days through Month 10 is calculated as: $14 \times (\text{total number of medication} \text{ days on the same days as planned non-scheduled OL rimegepant dosing days through Month 10 in the on-OL rimegepant efficacy analysis period)/(total number of planned non-scheduled OL rimegepant dosing days through Month 10 in the on-OL rimegepant efficacy analysis period).$

The table of medication days per month on planned scheduled OL rimegepant dosing days through Month 10 is provided, and summarizes parameters descriptively as continuous variables for the OL rimegepant migraine analysis set by treatment group/OL rimegepant and overall for the following medications:

- Any medication: rimegepant or acute migraine medication (triptan, ergotamine, or other)
- Rimegepant or acute migraine-specific medication (triptan or ergotamine)
- Rimegepant and acute migraine medication
- Rimegepant and acute migraine-specific medication
- Rimegepant only (i.e., no acute migraine medication)
- Acute migraine medication
- Acute migraine medication only (i.e., no rimegepant)
- Acute migraine-specific medication
- Acute migraine-specific medication only (i.e., no rimegepant or other medication)
- Other medication
- Other medication only (i.e., no rimegepant or acute migraine-specific medication).

The table of medication days per month on planned non-scheduled OL rimegepant dosing days through Month 10 is also provided, and summarizes parameters analogously.

6.4 Safety

Safety analyses are provided according to analysis period and analysis set:

- On-DBT safety for the DBT safety analysis set by treatment group
- Post-DBT pre-OL rimegepant safety for the interim safety analysis set by treatment group and overall
- On-OL rimegepant safety for the OL rimegepant safety analysis set by treatment group/OL rimegepant and overall
- On-DB or OL rimegepant safety for the DB or OL rimegepant safety analysis set by treatment group/OL rimegepant and overall
- Follow-up safety for the follow-up safety analysis set by treatment group/OL rimegepant status and overall.

Treatment group is as-treated treatment group according to Section 4.2.

Safety parameters include the following: deaths; AEs; laboratory tests; vital signs; physical measurements; electrocardiograms (ECGs); and Columbia-Suicidality Severity Rating Scale (C-SSRS.

Measurements are slotted into analysis periods and analysis visits using the following steps:

- 1) Measurements are slotted into the pretreatment, on-treatment safety, and follow-up safety analysis periods.
- 2) Measurements are slotted into analysis visits in the analysis periods listed in the previous step (see Table 5).
- 3) Measurements in the on-treatment safety analysis period are slotted further into the on-DBT, post-DBT pre-OL rimegepant, and on-OL rimegepant safety analysis periods.

Refer also to the Core SAP for details about measurement slotting. See Sections 6.2.5, 7.2, and 7.3 for definitions of baseline, analysis periods, and analysis visit windows, respectively.

6.4.1 Adverse Events

Refer to the Core SAP for the following: AE start and end date imputation; death date derivation; rules for counting and rounding in frequency tables; definition of AEs of special interest, and exposure-adjusted multiple occurrences of unique AEs; and TLF contents. An AE is considered to be related to study drug if the relationship to study drug is unlikely related, possibly related, or related.

Frequency tables of AEs by SOC and PT display AEs in descending order of overall frequency within SOC and PT, unless otherwise specified.

The by-subject listing of AEs (i.e., non-SAEs and SAEs) is provided for the enrolled analysis set.

6.4.1.1 Deaths

Deaths are identified from any of the following sources:

- AE CRF with any of the following: PT or reported term of "death"; outcome of fatal; "yes" response to the question "Did the AE result in death?"; complete or partially complete death date
- Screening Status CRF: death as reason for screen failure
- DB Subject Status CRF with any of the following: death as reason for DBT Phase noncompletion, or death as reason for not continuing to the next phase
- OLE Subject Status CRF with any of the following: death as reason for OLE Phase noncompletion; death as reason for not continuing to the Follow-up Phase.
- Follow-up Subject Status CRF: death as reason for Follow-up Phase non-completion.

The by-subject listing of deaths is provided for the enrolled analysis set.

6.4.1.2 AE Overviews

An AE overview frequency table displays the following categories without SOC and PT: any AE; mild AE; moderate AE; severe AE; AE related to study drug; AE leading to study drug discontinuation; SAE; SAE related to study drug; medication-overuse headache AE; hepatic-related AE; hepatic-related AE leading to study drug discontinuation; potential drug abuse AE; cardiovascular AE; and suicidality AE.

AE overview frequency tables are provided for the following safety analysis periods and analysis sets:

- On-DBT for the DBT safety analysis set
- Post-DBT pre-OL rimegepant for the interim safety analysis set
- On-OL rimegepant for the OL rimegepant safety analysis set
- On-DB or OL rimegepant for the DB or OL rimegepant safety analysis set
- Follow-up for the follow-up safety analysis set.

6.4.1.3 On-DBT AEs

Frequency tables of on-DBT AEs are provided by SOC and PT for the DBT safety analysis set for the following endpoints:

- AEs by worst intensity (secondary objective #8)
- AEs related to study drug by worst intensity
- AEs by relationship to study drug (related, possibly related, unlikely related, not reported)
- SAEs (secondary objective #8)
- AEs leading to study drug discontinuation (secondary objective #8)
- Hepatic-related AEs (secondary objective #9)
- Hepatic-related AEs leading to study drug discontinuation (secondary objective #9)
- Potential drug abuse AEs, displayed in alphabetical order by worst intensity and PT without SOC
- Cardiovascular AEs
- Suicidality AEs

Frequency tables of AEs by SOC and PT display AEs in descending order of rimegepant frequency within SOC and PT, unless otherwise specified.

6.4.1.4 On-OL Rimegepant AEs

Frequency tables of on-OL rimegepant AEs by SOC and PT are provided for the OL rimegepant safety analysis set for the following endpoints:

- AEs by worst intensity (secondary objective #8)
- AEs related to study drug by worst intensity
- AEs by relationship to study drug (related, possibly related, unlikely related, not reported)
- SAEs (secondary objective #8)
- AEs leading to study drug discontinuation (secondary objective #8).
- Hepatic-related AEs (secondary objective #9)
- Hepatic-related AEs leading to study drug discontinuation (secondary objective #9)
- Potential drug abuse AEs, displayed in alphabetical order by worst intensity and PT without SOC
- Cardiovascular AEs
- Suicidality AEs

6.4.1.5 On-DB or OL Rimegepant AEs

Frequency tables of on-DB or OL rimegepant AEs by SOC and PT are provided for the DB or OL rimegepant safety analysis set for below endpoints:

- AEs by worst intensity (secondary objective #8)
- SAEs (secondary objective #8)
- Exposure-adjusted multiple occurrences of unique AEs.

Calculations for on-DB or OL rimegepant exposure-adjusted multiple occurrences of unique AEs use an analysis period reference start date = DB or OL rimegepant start date, analysis period reference end date = DB or OL rimegepant last date + 7 days if the DB or OL rimegepant last date is nonmissing, and analysis period reference end date = DB or OL rimegepant end date if the DB or OL rimegepant last date is missing.

6.4.1.6 Follow-up AEs

Frequency tables of follow-up AEs are provided by SOC and PT for the follow-up safety analysis set for the following endpoints:

• AEs by worst intensity

• SAEs.

6.4.2 Laboratory Tests

Results are based on (1) external data from the central laboratory which reports both laboratory collection date and time, and (2) local data reported on Urine Pregnancy Test CRFs which capture only collection date. TLFs display results in Systeme Internationale (SI) units, if applicable.

Laboratory tests of clinical interest are collected at the following visits:

- Hematology: Screening; Baseline; Weeks 4, 8, 12, 24, and 52/EOT
- Serum chemistry: Screening; Baseline; Weeks 4, 8, 12, 24, and 52/EOT. Exceptions are for the following:
 - LFTs (ALT, AST, ALP, TBL, direct bilirubin, indirect bilirubin): All visits
 - Lipids (total cholesterol, high-density lipoprotein [HDL] cholesterol, low-density lipoprotein [LDL] cholesterol, triglycerides): Baseline; Weeks 24 and 52/EOT
- Urinalysis: Baseline; Week 52/EOT.

The following by-subject laboratory test listings are provided for the enrolled analysis set:

- Laboratory test results (SI units). The listing displays all test results over time for subjects with select findings (grade 3 to 4 laboratory test abnormalities or positive pregnancy tests) at any time point. A positive pregnancy test result is defined as serum or urine pregnancy test with either (1) "positive" character value, or (2) numeric value > ULN.
- LFT values and ratios to ULN (i.e., ALT, AST, TBL and ALP) for SI units. The listing displays all LFT results over time for subjects with select LFT elevations (ALT or AST > 3x ULN; ALP or TBL > 2x ULN) at any time point.

Refer to the protocol for laboratory tests of clinical interest, Refer to the Core SAP for toxicity grades and TLF contents. Laboratory test values are graded according to numeric laboratory test criteria using below toxicity grading scales:

• Common Terminology Criteria for Adverse Events (CTCAE) if available; otherwise according to Division of Acquired Immune Deficiency Syndrome (DAIDS) Table for Grading the Intensity of Adult and Pediatric Adverse Events. These are based on SI units.

6.4.2.1 Laboratory Test Worst Abnormalities

Frequency tables of the worst (highest) laboratory test abnormality for each graded laboratory test are provided for the following safety analysis periods and analysis sets:

- On-DBT for the DBT safety analysis set
- On-OL rimegepant for the OL rimegepant safety analysis set
- Follow-up for the follow-up safety analysis set.

Grade 3 to 4 results support secondary objective #8.

Frequency tables of laboratory test shift from baseline to the worst abnormality for each graded laboratory test are provided for the following safety analysis periods and analysis sets:

- On-DBT for the DBT safety analysis set
- On-OL rimegepant for the OL rimegepant safety analysis set.

6.4.2.2 LFT Elevations

LFT Elevations

Frequency tables of LFT elevations are provided for the following safety analysis periods and analysis sets:

- On-DBT for the DBT safety analysis set
- Post-DBT pre-OL rimegepant for the interim safety analysis set
- On-OL rimegepant for the OL rimegepant safety analysis set
- On-DB or OL rimegepant for the DB or OL rimegepant safety analysis set
- Follow-up for the follow-up safety analysis set.

Results support exploratory objective #9.

LFT Shifts from Baseline to Worst Elevation

Frequency tables of LFT shifts from baseline to the worst (highest) LFT elevation are provided for the following safety analysis periods and analysis sets:

- On-DBT for the DBT safety analysis set
- On-OL rimegepant for the OL rimegepant safety analysis set.

Exposure-adjusted Cumulative LFT Elevations

Frequency tables of exposure-adjusted cumulative LFT elevations are provided for the following safety analysis periods and analysis sets:

• On-DB or OL rimegepant for the DB or OL rimegepant safety analysis set.

Calculations use the same analysis period reference start and end dates as corresponding exposure-adjusted AEs (see Section 6.4.1.5).

Time to First LFT Elevation

Frequency tables of time to first LFT elevation are provided for subjects with select LFT elevations (ALT > 3x ULN; AST > 3x ULN; ALT or AST > 3x ULN) for the following safety analysis periods and analysis sets:

- On-DB or OL rimegepant for the DB or OL rimegepant safety analysis set with on-DB or OL rimegepant LFT elevations
 - Time categories are: ≤ 2 , > 2 to ≤ 4 , > 4 to ≤ 8 , > 8 to ≤ 12 , > 12 to ≤ 16 , > 16 to ≤ 20 , > 20 to ≤ 24 , > 24 to ≤ 28 , > 28 to ≤ 32 , > 32 to ≤ 36 , > 36 to ≤ 40 , and > 40 weeks.
 - Time to elevation is calculated as (LFT collection date DB or OL rimegepant start date + 1)/7.

LFT Plots

Evaluation of drug-induced serious hepatotoxicity (eDISH) scatter plots are provided for the following safety analysis periods and analysis sets:

- On-DBT for the DBT safety analysis set by treatment group
- On-OL rimegepant for the OL rimegepant safety analysis set by treatment group/OL rimegepant.

By-subject longitudinal LFT plots are provided for the safety analysis set with select LFT elevations in any safety analysis period. Study weeks are defined as study day/7, where study day is derived from the laboratory test collection date (see Section 7.3). Each figure also displays DB study drug dosing days and OL rimegepant dosing days using symbols along the x-axis (see Section 9.4), and denotes additional study milestones (e.g., start of the on-DBT safety analysis period, start of the on-OL rimegepant safety analysis period, and start of the follow-up safety analysis period) using vertical lines with their corresponding descriptions in footnotes.

6.4.2.3 Laboratory Test Changes from Baseline over Time

The table of values and changes from baseline in all hematology and serum chemistry laboratory tests is provided by treatment group and overall for the safety analysis set at the following time points: baseline; each scheduled visit through Week 12 and EOT in the on-DBT safety analysis period; each scheduled visit after Week 12 through Week 52 and EOT in the on-OL rimegepant safety analysis period; and Follow-up Week 2 in the follow-up safety analysis period. Results for overall are displayed only at baseline and time points in the on-OL rimegepant and follow-up safety analysis periods.

Note that scheduled visits vary according to laboratory test.

Refer to the Core SAP for (1) handling multiple values in an analysis visit window or on the same laboratory test collection date, and (2) deriving the EOT value in an on-treatment safety analysis period.

6.4.3 Vital Signs and Physical Measurement

Vital signs include systolic blood pressure, diastolic blood pressure, heart rate, temperature, and respiratory rate. Physical measurements include height, weight, and body mass index (BMI). These parameters are measured with a date at the following visits: Screening; Baseline; Weeks 4,

8, 12, 16, 20, 24, 28, 32, 36, 40, 44, 48, and 52/EOT; and Follow-up Week 2. Height is measured at the Screening Visit only.

Refer to the Core SAP for TLF contents.

6.4.3.1 Vital Sign and Physical Measurement Changes from Baseline over Time

The table of values and changes from baseline in vital sign and physical measurement parameters is provided by treatment group and overall for the safety analysis set at the following time points: baseline; each scheduled visit through Week 12 and EOT in the on-DBT safety analysis period; each scheduled visit after Week 12 through Week 52 and EOT in the on-OL rimegepant safety analysis period; and Follow-up Week 2 in the follow-up safety analysis period. Results for overall are displayed only at baseline and time points during the on-OL rimegepant and follow-up safety analysis periods.

Refer to the Core SAP for (1) handling multiple values in an analysis visit window or on the same measurement date, and (2) deriving the EOT value in an on-treatment safety analysis period.

6.4.3.2 Vital Sign and Physical Measurement Abnormalities

Frequency tables of vital sign and physical measurement abnormalities are provided for the following safety analysis periods and analysis sets:

- On-DBT for the DBT safety analysis set
- On-OL rimegepant for the OL rimegepant safety analysis set
- Follow-up for the follow-up safety analysis set.

6.4.4 Electrocardiograms

ECG parameters include QRS, PR, QT, QTcB, QTcF, and ventricular heart rate. ECGs are measured with assessment date on ECG CRFs at the following visits: Screening; Baseline; Weeks 4, 16, 24, and 52/EOT; and Follow-up Week 2.

Refer to the Core SAP for TLF contents.

6.4.4.1 ECG Changes from Baseline over Time

The table of values and changes from baseline in ECG parameters is provided by treatment group and overall for the safety analysis set at the following time points: baseline; each scheduled visit through Week 12 and EOT in the on-DBT safety analysis period; each scheduled visit after Week 12 through Week 52 and EOT in the on-OL rimegepant safety analysis period; and Follow-up Week 2 in the follow-up safety analysis period. Results for overall are displayed only at baseline and time points in the on-OL rimegepant and follow-up safety analysis periods.

Refer to the Core SAP for (1) handling multiple values in an analysis visit window or on the same measurement date, and (2) deriving the EOT value in an on-treatment safety analysis period.

6.4.4.2 ECG Abnormalities

Frequency tables of ECG abnormalities are provided for the following safety analysis periods and analysis sets:

- On-DBT for the DBT safety analysis set
- On-OL rimegepant for the DB or OL rimegepant safety analysis set
- Follow-up for the follow-up safety analysis set.

ECG abnormalities are presented together with vital sign and physical measurement abnormalities in the same tables (see Section 6.4.3.2).

6.4.5 C-SSRS

The C-SSRS is a clinician administered questionnaire used to help establish immediate risk of suicide. The C-SSRS is administered at early termination and all visits except Pre-randomization. At the Screening Visit, the recall period for completing is 12 months for suicidal ideation and 10 years for suicidal behavior; at all other visits, the recall period for completing the C-SSRS is since the last visit.

Refer to the Core SAP for calculation of C-SSRS parameters.

Frequency tables of C-SSRS suicidality are provided for the following safety analysis periods and analysis sets:

- On-DBT for the DBT safety analysis set
- On-OL rimegepant for the OL rimegepant safety analysis set
- Follow-up for the follow-up safety analysis set.

Refer to the Core SAP for calculation of C-SSRS parameters and TLF contents.

6.4.6 Safety Narrative Subject Identifiers

The by-subject listing of safety narrative subject identifiers is provided for the following select events as columns:

- Death in any analysis period for the enrolled analysis set
- SAE on DB or OL rimegepant or during follow-up for the DB or OL rimegepant safety analysis set
- AE leading to study drug discontinuation in any analysis period for the DB or OL rimegepant safety analysis set

- Event of special interest on DB or OL rimegepant for the DB or OL rimegepant safety analysis set:
 - \circ ALT or AST > 3x ULN
 - ALT or AST \ge 3x ULN and \ge 2x baseline
 - ALT or AST > 3x ULN concurrent with TBL > 2x ULN
 - \circ TBL > 2x ULN
 - Select hepatic-related AE, i.e., PT containing cirrhosis, hepatic failure, hepatitis, jaundice, or liver failure
 - Suicidality AE.

Refer to the Core SAP for additional details.

6.5 Outcomes Research

Analyses are based on as-randomized treatment group for the DBT efficacy analysis sets.

Outcomes research questionnaires MSQoL, MIDAS, and EQ-5D-5L are assessed using the eDiary at Baseline, Week 12, Week 24, and Week 52.

Measurements are slotted into analysis periods and analysis visits using the eDiary finding date and the following steps:

- 1) Measurements are slotted into the pretreatment, DBT outcomes research, and OL rimegepant outcomes research analysis periods.
- 2) Measurements are slotted into analysis visits in the analysis periods listed in the previous step (see Table 5).

Refer also to the Core SAP for details about measurement slotting. See Sections 6.2.5, 7.2, and 7.3 for definitions of baseline, analysis periods, and analysis visit windows, respectively.

By-subject listings of outcomes research questionnaires (i.e., MSQoL, MIDAS, and EQ-5D-5L) are provided for the enrolled analysis set. The listing displays values and changes from baseline for the following: MSQoL domain scores; MIDAS total, absenteeism, and presenteeism scores; EQ-5D-5L VAS score.

Refer to the Core SAP for the following: detailed descriptions of these questionnaires and rating scales; calculating scores and imputing missing data; deriving categories; handling multiple questionnaires or rating scale values in an analysis visit window or on the same assessment date; and TLF contents.

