 - Tablets per month are assessed by the number of 4-week (28-day) intervals in which a subject exceeded select tablet counts from the DB study drug start date to the DB study drug end date, where the number of 4-week intervals are consecutive (see Section 6.3.1.1 for months). For example, suppose a subject takes 20 tablets through 4 weeks, 10 tablets after 4 weeks to 8 weeks, and 25 tablets after 8 weeks to 12 weeks. Thus, this subject is not considered to have taken ≥ 14 tablets (more than EOD frequency) per month for 3 consecutive months.
- > 1 DB tablet taken on any 1 day
- ≥ 1 non-scheduled DB study drug dosing day (see Section 9.4)
- Incorrect DB study drug taken
 - All the time. Defined as as-treated treatment group not equal to as-randomized treatment group, i.e., any of the following:
 - Subjects randomized to rimegepant who took (1) ≥ 1 tablet from a DB placebo wallet, and (2) no tablets from a DB rimegepant wallet
 - Subjects randomized to placebo who took (1) ≥ 1 tablet from a DB rimegepant wallet, and (2) no tablets from a DB placebo wallet.
 - At least once. Defined as any of the following:
 - Subjects randomized to rimegpant who took ≥ 1 tablet from a DB placebo wallet
 - Subjects randomized to placebo who took ≥ 1 tablet from a DB rimegepant wallet.
- Time on study drug > 14 weeks.

Results for all categories are displayed, even those with 0 counts.

OL Rimegepant Treatment Compliance

The by-subject listing of OL rimegepant treatment compliance is provided for the safety analysis set, and displays results for OL rimegepant treatment compliance parameters in separate columns: average DB exposure (tablets per month; see Section 6.2.6.1); percentage for OL rimegepant tablet count compliance; flags for the other parameters ("Y" or missing).

The frequency table of OL rimegepant treatment compliance is provided by treatment group for the safety analysis set, and displays the following categories:

- OL rimegepant tablet count compliance ≥ 80% from OL rimegepant start to later of last scheduled OLE Phase visit or OL rimegepant end. Tablet count compliance is derived as 100 × cumulative OL rimegepant exposure/required cumulative OL rimegepant exposure, where
 - Cumulative OL rimegepant exposure is defined in Section 6.2.6.1.
 - Required cumulative OL rimegepant exposure is derived as follows:

- Let n = OL maxdate OL rimegepant start date + 1.

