6.5.1 MSQoL

The MSQoL consists of 14 items across the following 3 domains: (1) restrictive role function, (2) preventative role function and (3) emotional function.

Descriptive Analyses

The table of values and changes from baseline in scores is provided by treatment group and overall for each domain for the DBT efficacy analysis set at the following time points: baseline; Week 12 of the DBT outcomes research analysis period; Week 24 and Week 52 in the OL rimegepant outcomes research analysis period. Results for overall are displayed only at baseline and time points in the OL rimegepant outcomes research analysis period. Results support exploratory objective #8.

The frequency table of MSQoL domain score reduction from baseline categories is provided by treatment group and overall for the DBT efficacy analysis set at the following time points: Week 12 of the DBT outcomes research analysis period; Week 24 and Week 52 in the OL rimegepant outcomes research analysis period. Results for overall are displayed only at time points in the OL rimegepant outcomes research analysis period.

Treatment Group Comparisons

Analyses of each domain are based on the DBT efficacy analysis set with paired data, i.e., nonmissing domain scores at both baseline and Week 12 of the DBT outcomes research analysis period.

For each domain, treatment groups are compared using a linear regression model with the following attributes:

- Variables: Week 12 change from baseline in the score as the dependent variable; baseline score as a covariate; treatment group and randomization stratum as fixed effects.
- SE estimation method: See Section 6.3.1.1..

The table provides n (i.e., number of subjects with paired data) and the following model estimates for each domain:

- LSM change from baseline at Week 12, SE, and 95% CI for each treatment group
- Difference in LSM changes from baseline at Week 12 between each rimegepant treatment group and placebo (rimegepant placebo), SE, 95% CI, and p-value.

Results for the restrictive role function support secondary objective #5, whereas results for the other domains support exploratory objective #8.

See Section 9.3.2 for example SAS code. Model estimates by randomization stratum (yes, no) are presented in the same table, using additional linear regression models that exclude randomization stratum as a fixed effect.

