6.5.2 MIDAS

The MIDAS is a retrospective, patient-administered, 5-item questionnaire that measures headache-related disability as lost time due to headache from paid work or school, household work, and non-work activities.

Descriptive Analyses

The table of values and changes from baseline in total, absenteeism, presenteeism, and item scores is provided, and has a similar format as the one described in Section 6.5.1.

Results support exploratory objective #8.

Treatment Group Comparisons

Analyses of each score (total, absenteeism, presenteeism) are based on the DBT efficacy analysis set with scores at both baseline and Week 12 of the DBT outcomes research analysis period.

For each score, treatment groups are compared using a linear regression model with the same attributes as the one described in Section 6.5.1. The table has the same format.

Results for the total score support secondary objective #6, whereas results for the other scores support exploratory objective #8.

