6.5.3 EQ-5D-5L

The EQ-5D-5L is a 2-part assessment questionnaire of the subject's current health. In the first part, subjects rate their current level of function in 5 dimensions: mobility, self-care, usual activities, pain/discomfort, and anxiety/depression. In the second part, subjects rate their health on a VAS scale from 0 (worst imaginable health) to 100 (best imaginable health).

Descriptive Analyses

The table of values and changes from baseline in the VAS and utility index scores is provided, and has a similar format as the one described in Section 6.5.1. The utility index score is calculated from the official Japanese tariff based on time trade-off data.³

The frequency table of EQ-5D-5L dimension function level is provided by treatment group and overall for the DBT efficacy analysis set at the following time points: baseline; Week 12 of the DBT outcomes research analysis period; Week 24 and Week 52 of the OL rimegepant outcomes research analysis period. Results for overall are displayed only at baseline and time points in the OL rimegepant outcomes research analysis period.

Results support exploratory objective #8.

Treatment Group Comparisons

Analyses are based on the DBT efficacy analysis set with VAS scores at both baseline and Week 12 of the DBT outcomes research analysis period.

Treatment groups are compared using a linear regression model with the same attributes as the one described in Section 6.5.1. The table has the same format.

Results support secondary objective #7.

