7.3 Analysis Visit Windows

Refer to C4951021 Protocol Section 4.3 (Tables 1 and 2) for the schedule of assessments.

Refer to the Core SAP for defining randomization days, study days, rimegepant study days, and follow-up days in Phase 2/3/4 multiple-dose studies with both DBT and OLE Phases.

Analysis visit windows are shown in Table 5.

Table 5 Analysis Visit Windows

Analysis Period		Analysis Day	
Analysis Visit	Abbreviation in Listings	Analysis Visit Window	Target Day
Pretreatment	PRETRT	Randomization Day	
Screening *		≤ -7	
Pre-randomization *	Prerand	-6 to -1	
Baseline *		1	
Post-randomization @	Postrand	≥ 2	
Outcomes Research /On- treatment Safety	Outcomes Research: DBT or OLRMG/ Safety: DBT, INT, or OLRMG	Study Day	
Week 2		2 to 21	14
Week 4		22 to 42	28
Week 8		43 to 70	56
Week 12		71 to 91	84
Week 14		92 to 105	98
Week 16		106 to 126	112
Week 20		127 to 154	140

Analysis Period		Analysis Day	
Analysis Visit	Abbreviation in Listings	Analysis Visit Window	Target Day
Week 24		155 to 182	168
Week 28		183 to 210	196
Week 32		211 to 238	224
Week 36		239 to 266	252
Week 40		267 to 294	280
Week 44		295 to 322	308
Week 48		323 to 350	336
Week 52		351 to 378	364
Extension @		≥ 379	
Follow-up Safety	FU	Follow-up Day	
Follow-up Week 2	FU Week 2	8 to 35	14
Follow-up Extension @	FU Ext	≥ 36	

* For subjects in the enrolled analysis set excluded from the full analysis set, the visit label is used for slotting. @ Denotes an extended visit in the analysis period and is displayed only in listings

Study days are used to define analysis visit windows in all analysis periods. Follow-up days are used to define analysis visit windows in the follow-up safety analysis period.

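### The Week 12 questionnaire window closes at Day 91 only because of a Week 14 safety visit; unless the Core SAP overrides this, later double-blind scores leave the comparisons for secondary objectives 5 to 7

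*SAP*

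**What the plan says.** The three questionnaires have one post-baseline collection point in the double-blind phase, Week 12; the next are Weeks 24 and 52. SAP Section 6.5: "Outcomes research questionnaires MSQoL, MIDAS, and EQ-5D-5L are assessed using the eDiary at Baseline, Week 12, Week 24, and Week 52".

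Assignment to a visit is by date: "Measurements are slotted into analysis periods and analysis visits using the eDiary finding date and the following steps". Scores go first into an analysis period, then into a Table 5 visit. The Table 5 footnote uses the visit label only for enrolled subjects outside the full analysis set.

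Table 5 has a single block headed "Outcomes Research /On- treatment Safety". In it, Week 12 is study days 71 to 91, Week 14 is 92 to 105 and Week 16 is 106 to 126.

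The treatment comparisons need a Week 12 value. For MSQoL (Section 6.5.1) the requirement is "nonmissing domain scores at both baseline and Week 12 of the DBT outcomes research analysis period"; for MIDAS (Section 6.5.2), "DBT efficacy analysis set with scores at both baseline and Week 12 of the DBT outcomes research analysis period"; for EQ-5D-5L (Section 6.5.3), "DBT efficacy analysis set with VAS scores at both baseline and Week 12". These are secondary objectives 5 to 7, and Section 5 places them in the hierarchy at 2-sided 0.05.

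Section 3.2 gives outcomes research a treatment policy strategy, under which observed values are kept whether or not study drug was stopped. Section 6.5 refers to the Core SAP for further slotting details, and Section 7.2 refers to it for the definition of the outcomes research periods.

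**The concern.** A visit window separates competing scheduled measurements. No questionnaire competes with Week 12 until Week 24, yet the window is cut at Day 91 to make room for Week 14. On the stated schedule, a double-blind score on Days 92 to 105 is most naturally a late Week 12 assessment. It is filed under a visit for which Section 6.5 plans no outcomes research summary.

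The subject then has no Week 12 score and leaves the paired comparison. The tightest late limit thus falls on the only questionnaire time point with a treatment comparison. The laboratory, vital sign and ECG tables in Section 6.4 also have an end-of-treatment time point that can catch an out-of-window value; the outcomes research tables have none.

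At stake is avoidable missing data in three hierarchically tested endpoints. The loss also fits poorly with a strategy of using all observed values, although that strategy is worded around drug discontinuation, so this is a tension and not a formal contradiction.

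**Working it through.** **1. Rebuild Table 5.** Inputs: the target days in Section 7.3. Rule: each upper limit is the midpoint of adjacent targets, the first window opens on Day 2, and the last closes at target + 14. This reproduces all 15 on-treatment windows exactly. Around Week 12:
- Week 8 upper limit: (56 + 84)/2 = 70
- Week 12 upper limit: (84 + 98)/2 = 91
- Week 14 upper limit: (98 + 112)/2 = 105

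Day 91 therefore comes from the Week 14 target, Day 98. The next questionnaire target is Day 168, which is 84 days after Day 84.

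**2. Compare the three questionnaire visits.**

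| Visit | Target | Window | Days before / after target |
|---|---|---|---|
| Week 12 | 84 | 71 to 91 | 13 / 7 |
| Week 24 | 168 | 155 to 182 | 13 / 14 |
| Week 52 | 364 | 351 to 378 | 13 / 14 |

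The early side is the same at all three; only the late side at Week 12 is shorter.

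**3. Pass single days through the windows.** Day 91 is Week 12. Days 92 and 105 are Week 14. Days 106 and 126 are Week 16. Day 127 is Week 20. From Day 92 onward no label supplies a Week 12 value.

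**4. Size.** The late share is not in the documents, so 1 to 5% is assumed. No paired questionnaire count is given either, so the 225 evaluable per arm is borrowed from Section 5.
- Subjects lost per arm: 0.01 × 225 = 2.25; 0.05 × 225 = 11.25
- Standard error ratio 1/√(1 − f): 1/√0.99 = 1.005; 1/√0.95 = 1.026

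**5. Power, as illustration.** The only stated power, roughly 80%, is for the primary endpoint. It reproduces: 1/(3.75 × √(2/225)) = 2.828, and Φ(2.828 − 1.960) = 80.7%. None is stated for the questionnaires. If one had 80% power at 225 per arm, its noncentrality would be 1.960 + 0.842 = 2.802. A 5% loss gives 2.802 × √0.95 = 2.731, and Φ(2.731 − 1.960) = 78.0%.

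**The case against.** **The Core SAP may settle it.** It holds further slotting details, the handling of multiple or missing questionnaire values, and the period definitions. It could contain an override. Nothing in the supplied text says that it does, but the point is conditional on this.

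**Late scores may be rare.** Day 91 already allows a week, and Section 2.1 says the double-blind phase lasts up to 12 weeks. The supplied protocol is for study C4951022 (acute treatment), while the SAP is for C4951021 (prevention), so the permitted Week 12 visit window cannot be checked. This stands: the frequency is unknown.

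**The windows are defensible as written.** They are prespecified, contiguous and follow one rule, and a tight window suits a time-specific endpoint. That is a reason against a large extension, but it does not explain why Week 12 should be tighter than Weeks 24 and 52.

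A reader might infer more than the documents support:
- **That the SAP expects dosing past 14 weeks.** The entry "Time on study drug > 14 weeks" in Section 6.2.6.2 is a row in a compliance table displayed even with zero counts. It can detect late dosing but does not forecast it.
- **That every late questionnaire is lost through Table 5.** A score dated after open-label start may be assigned to the open-label period first, which no change to the windows would repair.
- **That the scores vanish.** They remain in the by-subject listings; they are lost only from the Week 12 comparisons.
- **That the midpoint rule on questionnaire visits alone is the remedy.** It would close Week 12 at (84 + 168)/2 = Day 126, 42 days after target, and extend Week 24 to (168 + 364)/2 = Day 266. That is too loose for endpoints tied to a week.

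**Conclusion.** The mechanism holds on the supplied text. Questionnaires inherit safety windows, and a double-blind score on Day 92 or later leaves the paired Week 12 comparisons for secondary objectives 5 to 7. The effect is probably small, within the range shown above, and rests on an assumed late share, a borrowed denominator and the absence of a Core SAP override. The documents do not establish bias between arms or an effect on type I error. The primary endpoint is untouched, and the three tests carry inferential weight only if the primary and secondary endpoints 1 to 4 are significant. This is a cheap improvement and not an analysis error.

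**What to change.** First confirm whether the Core SAP already has questionnaire-specific slotting. If it does not, add separate outcomes research rows to Table 5 before unblinding, which Section 2.3 ties to the primary completion database lock:
- Week 12 = study days 71 to 98, the same 13 days before and 14 days after target as Weeks 24 and 52. If a wider limit is wanted, go no further than Day 105, which absorbs the present Week 14 window.
- Restrict it to the double-blind outcomes research period, so that open-label scores stay out.
- Where several values qualify, take the one closest to Day 84, and align this with the Core SAP rule for multiple values.
- Leave the Week 24 and Week 52 windows unchanged.

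The rule depends on dates only, so it can be set without reference to outcomes. The cost is one extra block of rows in Table 5 and a slightly looser Week 12 time point.
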